#### 5.1.3 Laser Doppler Flowmetry (LDF)

LDF measurements will be taken at post-grafting for assessment of tissue perfusion.

Details of use and measurement of the LDF is described in Section 6.2.5.

#### 5.1.4 Dental Impressions of Maxilla

All subjects will have an upper, maxillary, impression taken for a healing palatal stent that will be protective for the patient post-surgery at the graft donor site.

#### 5.1.5 Harvest Biopsy

For subjects randomized to the EVPOME arm of the study, during visit 2, surgeon co-investigators will extract a single 6 mm circular punch biopsy for EVPOME manufacturing. Detailed handling of the EVPOME is described in Section 5.2.

#### 5.1.6 Biopsy and Specimen Handling

All subjects will be prepped and draped in a sterile fashion prior to intraoral biopsies. Anesthesia will be obtained by local infiltrations and/or blocks, and tissue will be harvested using a 6 mm punch. If bleeding is not controlled under gauze tamponade, a hemostatic collagen sponge will be placed and a cyanoacrylic dressing will be applied topically over the wound. Subjects will be given routine post-operative instructions to include a prescription for analgesia. The 6 mm biopsy specimen will be placed in a specifically prepared transport medium containing 500.0 ml DPBS (Dulbecco's Phosphate Buffered Saline) w/o  $\text{Ca}^{2+}$  or  $\text{Mg}^{2+}$  and containing 0.54 g D-Glucose, 62.5 mg Gentamicin and 500.0  $\mu\text{g}$  Fungizone. The biopsy will be immediately delivered to the Clinical Tissue Manufacturing Laboratory (CTML) for oral keratinocyte dispersion and culture. The specimen will be labeled with pre-printed labels from the CTML with protocol number and subject study number.

### 5.1.5 Grafting

After the subject is anesthetized, the surgical site will be prepared leaving the underlying periosteum intact. The EVPOME or POM grafts (harvested from the palate at this same visit) will be sutured and assessed to assure they are immobile. Patients will be given standard post-operative instructions, analgesics, and antibiotics per standard of care.

### 5.1.6 Assessment of Graft Contracture

At each follow-up visit, the percent (%) graft contracture will be determined by linear measurements taken from the periphery of the standardized size graft.

### 5.1.7 Study Laboratory Evaluations

Histology and immunohistochemistry will be performed on each 2 mm circular graft biopsy taken at Week 4 at the site after laser Doppler measurement has been taken. Histology will consist of standard hematoxylin and eosin stain, while immunohistochemistry will be used to assess microvessels within the dermal matrix.

### 5.1.8 Observation

At each follow-up visit, the percent (%) epithelial coverage will be determined by linear measurements taken from the periphery of the graft.

### 5.1.9 Postoperative pain

Pain following the grafting procedure will be evaluated using a visual analog scale (VAS) at the time of palatal biopsy for the EVPOME and at the time of harvesting and grafting of the POM grafts.

### 5.1.10 X-rays/radiographs

If a current panoramic radiograph or full mouth series of periapical radiographs are not available, new ones will be obtained. Close proximity of the mental nerve canal, periapical (endodontic) lesions or other pathologies to the anticipated surgical site may contradict surgery. Radiographs taken in the past two years are sufficient to determine if surgery is contradictory.

## 5.2 Handling of Study Interventions

All of the AlloPatch® used in this study will be procured and stored by UM Clinical Tissue Manufacturing Laboratory (CTML) for use on this study. When subjects are randomized to EVPOME arm, AlloPatch® will be available to the study team in the Clinical Tissue Manufacturing Laboratory where EVPOME manufacturing will take place.

For subjects randomized to the EVPOME arm of the study, during Visit 2, surgeon co-investigators will extract a single 6 mm circular palatal punch biopsy for EVPOME manufacturing. In the case in which the subject wears an upper prosthesis the harvest biopsy will be taken from the retromandibular trigone region in the mandible. A member of the EVPOME manufacturing team will provide pre-labeled transportation vessels, a primary vessel containing transportation media in which the biopsy will be placed, and a secondary containment vessel into which the primary transportation vessel will be placed.

The surgeon and the EVPOME manufacturing technician will document the chain of custody by completing the transportation of punch biopsy record. The manufacturing technician will transport the biopsy and record to the Clinical Tissue Manufacturing Laboratory and begin EVPOME manufacturing. EVPOME manufacturing procedures provide detailed instructions for the manufacture, control, and release of the EVPOME product.

On the day that the EVPOME engraftment is to occur, the Principal Investigator, [name], or the Clinical Tissue Manufacturing Laboratory Manager will review the EVPOME manufacturing records and determine if the EVPOME meets required specifications (passing the sterility tests and satisfying the release criterion of glucose consumption over the last 24 hours) for engraftment. If the EVPOME is released by the Principal Investigator or the CTML Manager, the certificate of analysis is signed. The manufacturing staff will then transport the EVPOME to the surgeon in the surgical suite and attain site staff signature of receipt. If the EVPOME is determined to be unsuitable for engraftment, then there are two paths of accountability for the unused EVPOME. One of the following two paths will be used and documented on the EVPOME certificate of analysis:

1. The informed consent document allows research subjects to opt-in or opt-out of allowing excess tissues and EVPOME devices to be transferred to a University of Michigan tissue repository held by [name] (IRB approved HUM00035831). If a subject opts-in, then their unused cells and EVPOMEs will be de-identified, labeled, and transferred from the Clinical Tissue Manufacturing Laboratory to the Medical Science Research Building II where the PI, [name], has a research laboratory and the oral mucosa bank is housed.
2. If a subject opts-out, then their excess cells and EVPOMEs will be destroyed as biohazard waste by processing in an autoclave.

### 5.3 Concomitant Interventions

#### 5.3.1 Required Interventions

All standard surgical and post-operative standard medications and therapies will be performed.

#### 5.3.2 Prohibited Interventions

- Consumption of alcohol or use of alcohol-containing products
- Smoking
- Other interventions which may be questionable for use should be discussed with the Principal Investigator and/or surgeon prior to use, if able.

#### 5.4 Adherence Assessment

During each post-surgery visit, study subjects will be questioned on adherence to post-operative guidelines including dental hygiene, alcohol consumption, and smoking abstinence to assess correlation of these factors with graft contracture and revascularization.

### 6. CLINICAL AND LABORATORY EVALUATIONS

A defined table of study procedures by visit is listed in section 6.1. A narrative of these evaluations is described in section 6.2.

6.1 Schedule of Evaluations

Procedure	Visit 1 Screening	Visit 2 Harvest Biopsy	Visit 3 Base- line Intra-oral Graft	Visit 4 Post- Op	Visit 5 Follow-up	Visit 6 Biopsy and Follow-up	Visit 7 Follow-up	Visit 8 End of Study
Timeline (in reference to baseline)	-1 to -90 days	-2 to -40 days	Day 0	Week 1 +/- 3 days	Week 2 +/- 3 days	Week 4 +/- 1 week	Week 8 +/- 1 week	Week 24 +/- 1 week
Informed Consent and Inclusion/Exclusion	X							
Urine Pregnancy Test <small>*females of child bearing potential only</small>	X							
Randomization	X							
Medical/Dental History	X							
X-rays (if none have been taken in the past two years)	X							
Oral Examination	X			X	X	X	X	X
Pain Visual Analog Scale (VAS)	X	X	X	X	X	X	X	X
Clinic Assessments*	X				X	X	X	X
Intraoral Photographs	X	X ~	X	X	X	X	X	X
Dental Impressions	X							
Tissue Harvest Biopsy ~		X ~						
Graft Placement			X ∞					
Graft Biopsy						X		
Laser Doppler Flowmetry (LDF)					X	X	X	X
Laboratory Evaluations +						X		
Assess Adverse Events		X	X	X	X	X	X	X
Follow-up phone calls will occur at 9 and 12 months post-grafting.								

\*Clinic assessments may include: PPD, CAL, BOP, Mobility, keratinization, graft contracture, graft color, wound healing index,

~Harvest biopsy will be performed only on subjects randomized to the experimental EVPOME arm of the study

+Laboratory evaluations include: histology, immunohistochemistry

∞At this time the POM graft will be harvested from the donor palatal site and grafted to the recipient site

## 6.2 Evaluation Schedule

### 6.2.1 **Visit 1 Screening**

Subjects will be recruited through the Patient Admitting and Emergency Services (PAES) clinic in the U-M School of Dentistry in conjunction with MCOHR. All new patients are routed through PAES and assigned to specialty or undergraduate clinics. Most patients do not return to the PAES clinic, so we are not likely to have redundancy. PAES had 13,100 visits in 2003. It is estimated that 40% of the western population is missing 1 or more teeth (50% to be restored with implants for our purposes). Approximately 1/3 of them are in need of soft tissue oral mucosa grafts which is a very common procedure. This will give us a population from which to draw approximately 865 new patients per year. Of this group we need to recruit 60 subjects over two years from a potential pool of 1,730 patients. With an estimated enrollment of 1 out of 4 screened patients, we should have a pool of over 400 patients per year from which to select 30 subjects. Subjects will be recruited by full-time faculty members in the Department of Periodontics at the U-M School of Dentistry.

Informed consent will be obtained from each subject before any study-related procedures are performed. Screening and consenting procedures will be performed by the study staff on site at the clinic.

During the consenting process, the study staff will allow time for the subject to review the Informed Consent Form, ask questions, and make an informed decision (i.e. allow the subject to discuss with family etc.).

If the subject is willing and able to consent, the study staff will perform the study-specific procedures and evaluations to determine eligibility. Determination of eligibility will include review of subject-reported medical and dental history, an oral examination, and x-rays, if necessary. Subject weight will also be collected.

Medical and dental history will be questioned to determine any history of special conditions that may affect the subject during the study and its associated procedures. Potential study contraindications may include history of heart disease, relevant allergies, or the use of medications such as blood thinners. Concomitant medications will be updated throughout the trial. A visual analog scale of pain will be taken at this time for both group I and II,

Women of childbearing potential must agree to use a medically acceptable means of birth control and test negative on the Screening Visit urine pregnancy test. Intraoral photographs will also be taken.

Lastly, upper and lower jaw impressions will be taken for stent fabrication to protect the donor site and for use in LDF measurements

Subjects randomized to Group 1 (EVPOME), will be scheduled for Visit 2 to undergo a palatal punch biopsy/tissue harvesting which will be the source of autogenous cells used to make the cellular component of the EVPOME, within 14 days of determination. Subjects randomized to Group 2 (POM) will bypass Visit 2 and proceed to scheduling of harvesting of palatal donor tissue graft and intra-oral grafting at recipient site (Visit 3) upon completion of screening procedures.

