### Interventions and Duration

The outcomes data in patients treated with experimental EVPOME soft tissue intraoral grafting procedure will be compared to the outcomes in patients treated with POM, which is the standard of care procedure. Those randomized to the experimental group will undergo a small 6mm palatal punch biopsy. Keratinocytes extracted from the punch biopsy will be harvested and expanded *in vitro* then seeded onto the AlloPatch®. This process will take approximately 30 days depending on the period of time needed for cell amplification. EVPOME or POM will then be grafted onto the oral defect and secured with absorbable sutures. At Week 4, after grafting, a 2 mm punch biopsy will be taken to assess degree and maturity of keratinization and microvessel ingrowth.

Throughout the duration of the study, the subject will return for subsequent study visits to assess oral health and graft healing, contracture, and revascularization. The subjects will attend 7-8 scheduled study visits, one of which will be the grafting procedure, over a period of approximately 30 weeks. The post-operative follow-up period will include 5 study visits over approximately 24 weeks.

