#### 4.2 Exclusion Criteria

- 4.1.1. Subjects with a known sensitivity to agents used in AlloPatch® production including: Gentamicin, Cefoxitin, Lincomycin, Polymyxin B, and Vancomycin
- 4.1.2. Subjects with potential medical complications such as evidence of clinically significant (as defined by investigators) renal, hepatic, cardiac, endocrine, hematologic, autoimmune, or any systemic disease which may complicate execution of the protocol and/or interpretation of results, i.e. interfere with wound healing or be a poor candidate for general anesthesia, uncontrolled diabetic, renal failure etc.
- 4.1.3. Documented history of syphilis, HIV, Hepatitis B or C virus
- 4.1.4. Pregnant women or women planning to become pregnant or unwilling to abstain or use double barrier contraceptives during the course of the study
- 4.1.5. Known or suspected allergy to bovine (cow) protein or iodine
- 4.1.6. Current radiation therapy or history of radiation therapy treatment to the intraoral donor biopsy site or recipient site for graft placement.
- 4.1.7. Smoking or use of tobacco products within 6 months prior to screening (subjects who quit smoking > 6 months prior to screening will be considered former smokers)
- 4.1.8. History of either alcohol or drug abuse in the past 5 years
- 4.1.9. Participation in another clinical trial within 30 days of screening
- 4.1.10. Subjects taking medications that can result in gingival enlargement/overgrowth (Cyclosporine, Dilantin, calcium channel blockers)
- 4.1.11. Current use of a medication used to treat a thyroid disease.
- 4.1.12. Current use of intravenous anti-resorptive therapies or a history of intravenous antiresorptive therapies during the past 5 years
- 4.1.13. Prior successful or attempted graft placement at the study defect site
- 4.1.14. Any physical or mental condition which in the opinion of the Investigator or Medical Monitor may interfere with the subject's ability to comply with the study procedures

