#### 6.2.2 **Visit 2: Harvest Biopsy (EVPOME group only)**

At this time, a 6 mm in diameter supra-periosteal circular biopsy will be harvested for fabrication of the EVPOME from Group 1 subjects. Co-Investigators will perform the biopsy procedure. This biopsy will be performed at the school of dentistry research clinic. Intraoral photographs will also be taken at this time. A stent will be placed at this time if needed.

*Biopsy procedures:* All subjects will be prepped and draped in a sterile fashion prior to intraoral biopsies. Anesthesia will be obtained by local infiltrations and/or blocks. Tissue will be harvested using a 6mm punch. If bleeding is not controlled under gauze tamponade, a hemostatic collagen sponge will be placed and a cyanoacrylic dressing will be topically applied over the wound. Subjects will be given routine post-operative instructions to include a prescription for analgesia.

*Specimen handling:* The 6 mm biopsy specimen will be placed in a specifically prepared transport medium, containing 500.0ml DPBS (Dulbecco's Phosphate Buffered Saline) w/o  $\text{Ca}^{2+}$  &  $\text{Mg}^{2+}$  containing 0.54 g D-Glucose, 62.5 mg Gentamicin and 500.0  $\mu\text{g}$  Fungizone. The biopsy is immediately delivered to the CTML for oral keratinocyte dispersion and culture. The specimen will be labeled with pre-printed labels from the CTML with protocol number and subject study number.

A visual analog scale of pain will be taken at this time for group I and subjects will also be questioned about any adverse events.

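### The only scheduled pregnancy test is at screening, up to 90 days (POM) or about 54 days (EVPOME) before grafting; it is not repeated, and no rule says whether a randomized woman found pregnant is grafted.

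*Combined protocol and SAP*

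**What the plan says.** Section 6.2.1 sets the requirement at screening: "Women of childbearing potential must agree to use a medically acceptable means of birth control and test negative on the Screening Visit urine pregnancy test". In the 6.1 schedule the urine pregnancy test row, footnoted "females of child bearing potential only", has a single mark, under Visit 1. Inclusion criterion 4.1.6 asks for a negative urine test but does not tie it to the date of surgery.

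The exclusions in section 4.2 rule out "Pregnant women or women planning to become pregnant or unwilling to abstain or use double barrier contraceptives during the course of the study". Section 7 lists unforeseen harm to a pregnant woman or fetus among the possible risks.

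On timing, 6.1 allows Visit 1 from 1 to 90 days before grafting and the harvest biopsy from 2 to 40 days before. EVPOME subjects are scheduled for harvest "within 14 days of determination". POM subjects "will bypass Visit 2 and proceed to scheduling of harvesting of palatal donor tissue graft". On EVPOME manufacture, the synopsis says: "This process will take approximately 30 days depending on the period of time needed for cell amplification".

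On a pregnancy that occurs during the study, 6.2.12 provides for follow-up to its end and for reporting. Section 8 names HIV and cancer needing radiation therapy as reasons for discontinuation and then leaves the list open. It does not name pregnancy.

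**The concern.** Section 4.3 applies the eligibility criteria once, before randomization. The exposure comes later: anesthesia, the graft, and post-operative analgesics and antibiotics as standard care requires. A negative test from weeks earlier cannot show that the pregnancy exclusion still holds on the day of surgery. In the EVPOME arm the delay is built in, because the graft has to be grown.

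A woman in either arm who conceives in that interval could be grafted without anyone knowing she is pregnant. If she already knows and says so, the protocol does not tell the surgeon expressly whether to proceed.

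**Working it through.** **1. Is there any later check for pregnancy before grafting?**

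| Visit | Pregnancy test | What the text asks for |
|---|---|---|
| 1 Screening | Yes | Eligibility, history, impressions |
| 2 Harvest (EVPOME only) | None | Pain score; "subjects will also be questioned about any adverse events" |
| 3 Grafting | None | Pain score and adverse events, both arms |

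The grafting-day review in 5.2 is there to "determine if the EVPOME meets required specifications". It covers sterility and glucose consumption of the product, not the woman's status.

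**2. Age of the test at grafting, POM.** With Visit 2 skipped, only the Visit 1 window applies: 1 to 90 days. 90 / 7 = 12.9 weeks.

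**3. Age of the test at grafting, EVPOME, one biopsy.** Inputs are determination to harvest, 0 to 14 days (6.2.1), and harvest to graft, about 30 days (synopsis) up to 40 days (6.1). Assume determination falls on the Visit 1 date, which fits 6.1 marking randomization at Visit 1.

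- Lower end: 0 + 30 = 30 days.
- Upper end: 14 + 40 = 54 days; 54 / 7 = 7.7 weeks.
- If determination comes L days after the test, the maximum is min(54 + L, 90). The 90-day cap is reached at L = 90 − 54 = 36.

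**4. EVPOME, failed first device.** Section 6.2.3 allows a second biopsy. Assuming it is taken as soon as a 30-day manufacture fails, the interval is about 14 + 30 + 30 = 74 days, or 14 + 30 + 40 = 84 days if the second biopsy is 40 days before the graft.

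**5. What if pregnancy is found before Visit 3?** Section 4.2 governs entry. Section 6.2.12 covers follow-up and reporting. Section 8 could be stretched to include pregnancy through its open ending. None of the three says whether the graft is given or withheld.

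**6. Precision cost of withholding one graft.** Section 9.5 gives an SD of 0.65 mm, 30 per arm, a standard error of 0.17 and a margin of error of about 0.33 mm.

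- As planned: SE = 0.65 × √(1/30 + 1/30) = 0.1678; margin = 1.96 × 0.1678 = 0.329 mm, which reproduces the plan.
- With one subject lost: SE = 0.65 × √(1/30 + 1/29) = 0.1693; margin = 0.332 mm.
- Difference: 0.003 mm.

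**The case against.** The best counter-argument is that the intervals are outer limits. The synopsis expects about 30 weeks in total and about 24 after surgery, which leaves roughly 6 weeks (42 days) before the graft, and POM subjects go to scheduling once screening is complete. This is fair: 90 days is permitted, not typical. The same 90-day window formally covers EVPOME subjects too, so the contrast between arms depends on the derived 54 days. But a six-week-old test still does not show a woman's status on the day of surgery.

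Other safeguards exist. Contraception is required throughout the study, subjects are in contact with staff before grafting, and 6.3.4 requires intervention changes to be discussed with the Medical Monitor, which is a plausible route for withholding a graft. These lower the risk or help once a pregnancy is known. None of them detects one.

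The longest interval falls in the arm that receives standard care, and the documents name no specific fetal hazard. That limits the weight of the point. Still, the exclusion and the listed risk are the protocol's own, and they are not confined to one arm. Post-operative drugs are also less certain than 5.1.5 (Grafting) suggests, since 6.2.3 says only that they may be given.

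Finally, the consent pages and the Manual of Procedures were not available, and either might address a positive test. A test guarding against a listed risk belongs in the protocol schedule in any case.

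**Conclusion.** The gap is real. The one scheduled test can be up to 90 days old at grafting in POM and up to about 54 days old in the ordinary EVPOME pathway, or longer after a repeat biopsy. The 54 days is derived, not stated, and rests on determination falling on the Visit 1 date. No scheduled test would detect a pregnancy that began after screening, and the action on finding one is not expressly stated.

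The number of women of childbearing potential is not given, so the expected number of cases cannot be estimated. The sample size, power and error rate are untouched. This is an inexpensive safety improvement that should be made; it does not threaten the trial's conclusions.

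**What to change.** - In 6.1 and 6.2.3, add a repeat urine pregnancy test at Visit 3, before anesthesia and grafting, for women of childbearing potential in both arms.
- State that a woman who tests positive is not grafted, is followed under 6.2.12, and remains in the randomized population.
- As an editorial tidy-up, align the contraception wording in 6.2.1, which accepts any medically acceptable method, with the stricter exclusion in 4.2 (item 4.1.4), which already governs entry through 4.3.

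A further test at Visit 2 is optional. Under the same assumption the screening result is at most 14 days old at harvest, and a Visit 2 test would not replace one on the day of grafting.

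The cost is one dipstick per eligible woman at an existing visit: at most 66 even if every subject enrolled under 9.3 qualified. The downside is that a rare woman who tests positive gives no Week 4 graft data, in EVPOME after biopsy and manufacture. Section 9.3 already allows for 6 losses before Week 4 (66 − 6 = 60), and one loss from 30 per arm would widen the keratinized-tissue margin by only 0.003 mm.
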